7.5 Concomitant Medication

Throughout the trial investigators may prescribe any concomitant medications or treatments deemed necessary to provide adequate supportive care except for those listed in the exclusion criteria (see section 6.3.3). If these are required during the five days of IMP administration, the participant will be withdrawn from the trial treatment.

The following specific medications, other than the trial treatment, taken during the study will be recorded in the CRF:

- a) antiviral drugs
- b) antibiotics
- c) corticosteroids given after completion of trial treatment

8 SAFETY REPORTING

The definition of a serious adverse event (SAE) is problematic in the context of the ASAP trial since participants are likely to be critically ill patients and progression of pandemic influenza can lead to significantly life threatening and serious conditions, which are outcomes for this trial.

Events that are part of the natural history of the primary disease process or expected complications of critical illness will not be reportable as serious adverse events.

The principal investigator at a site will need to distinguish between an SAE that is possibly, probably or definitely related to treatment (i.e. a suspected adverse reaction (SAR) – see definition below) and an SAE that arises from disease progression or has another cause.

The study intervention (dexamethasone) is a commonly used drug for which the safety profile is well established. For this reason, only serious unexpected suspected adverse reactions (SUSARs) should be reported on an SAE form for this trial.

The trial will also capture other serious adverse events (SAEs), which are pre-specified outcomes in the trial. These will not be reportable on an SAE form but will be captured on the CRF and include the following:

- Death due to progression of the underlying disease or co-morbid illness
- Admission to the intensive care unit due to progression of the underlying disease or co-morbid illness
- Prolongation of hospital stay due to progression of the underlying disease or co-morbid illness

8.1 Definitions

8.1.1 Serious Adverse Event (SAE)

A serious adverse event is any untoward medical occurrence in a patient administered a medicinal product, which does not necessarily have to have a causal relationship with the treatment (the study medication) that at any dose:

- Results in death,
- Is life-threatening (NOTE: The term "life-threatening" in the definition of "serious" refers to an event in which the participant was at risk of death at the time of the event; it does not refer to an event which hypothetically might have caused death if it were more severe.)
- Requires inpatient hospitalisation or prolongation of existing hospitalisation,
- Results in persistent or significant disability/incapacity, or
- Is a congenital anomaly/birth defect.
- Other important medical events (NOTE: Other events that may not result in death are not life threatening, or do not require hospitalisation, may be considered a serious adverse event when, based upon appropriate medical judgement, the event may jeopardise the patient and may require medical or surgical intervention to prevent one of the outcomes listed above.)

8.1.2 Serious Adverse Reaction (SAR)

All untoward and unintended responses to a medicinal product related to any dose.

The phrase "responses to a medicinal product" means that a causal relationship between a study medication and an AE is at least a reasonable possibility, i.e., the relationship cannot be ruled out.

All cases judged by either the reporting medically qualified professional or the sponsor as having a reasonable suspected causal relationship to the trial treatment qualify as adverse reactions.

8.1.3 Expected Serious Adverse Reactions (Expected SAR)

An adverse reaction, the nature or severity of which is consistent with the applicable product information.

8.1.4 Suspected Unexpected Serious Adverse Reactions (SUSARs)

A serious adverse reaction, the nature or severity of which **is not** consistent with the summary of product characteristics. Dexamethasone is an established drug with a well-known safety profile and therefore the occurrence of SUSARs in this trial is unlikely.

8.2 Reporting procedure

Serious unexpected adverse reactions (SUSARs) are expected to be rare in this trial, however **all** SUSARs should be reported on an SAE form within 24 hours of being made aware of the event to the Sponsor.

The fax number for reporting of SUSARs will be supplied to trial sites once the decision to activate the trial has been made.

[figure not shown]
All other serious adverse events and serious adverse reactions will not be reported. Where they are a prespecified outcome for the trial they will be collected on the CRF.

The flow chart in

Figure **4** should be used to determine whether an SAE requires reporting on an SAE form.

* the event is not consistent with the summary of product characteristics

9 STATISTICAL CONSIDERATIONS

A separate detailed statistical analysis plan will be written and approved by the Trial Steering Committee during the set up phase. The trial is planned in anticipation of a high severity pandemic; this represents the most challenging situation for trial execution and also the situation in which the trial results might have the largest public health impact. At the outset of a pandemic, its severity will not necessarily be accurately appreciated. The statistical plan therefore includes the flexibility to address pandemics of different severity. A review of pandemic severity will be conducted by the TSC as the pandemic unfolds. Decisions regarding the final analysis plan and final primary outcome will rest with the TSC. A summary of the plan is described below.

9.1 Description of Statistical Methods

We will compare numbers, age and sex of randomised participants with aggregate summary data of all patients admitted to hospital with influenza-like illness during the study period. We will compare baseline characteristics of the randomised arms using appropriate descriptive statistics. Between-group comparisons for primary and secondary outcomes will be conducted using an intention-to-treat (ITT) approach, implemented using appropriate regression models, and with results presented as point estimates such as a ratio or difference comparing dexamethasone with placebo, with 95% confidence intervals, and exact p-values. Secondary analyses will include additional adjustment for variables displaying an important imbalance at baseline. We anticipate little, if any, missing primary outcome data and therefore will use ITT without imputation as the main approach, and will investigate the influence of any missing data in sensitivity analyses, including multiple imputation. A definition of the pandemic as high, moderate or low severity is expected soon after the end of the first wave, and analysis of the appropriate primary outcome, and such secondary outcome data as are available, will then ensue in time to inform subsequent pandemic waves. All analyses will be conducted using Stata version 11.2 or higher, or MLwiN 2.10 or higher.

It is possible that a small number of participants will be randomised more than once. We will examine baseline (at first randomisation) characteristics and previous treatment allocation(s) of participants randomised more than once using appropriate descriptive statistics. The primary analysis will use treatment allocation and date of the first randomisation. In sensitivity analyses, we will (1) further adjust for variables associated with multiple randomisation (baseline characteristics and initial treatment allocation), and (2) use treatment allocation and date of the last randomisation.

High Severity Pandemic

In a high severity pandemic, the primary composite outcome is admission to intensive care or death by Day 30, and will be analysed using generalised linear modelling for binary outcomes, also allowing for stratification by site. Additionally, death will be reported alone as a secondary outcome.

Low/Moderate Severity Pandemic

In a **low/moderate severity pandemic**, the **primary outcome is time to hospital discharge**, **rightcensored at 30 days**, **and** will be analysed using appropriate (dependent on distribution of the outcome) time-to-event regression modelling, also allowing for stratification by site and for the occurrence of death prior to hospital discharge as a competing event.

Pre-planned sub-group analyses will be conducted for the primary outcome based on the following baseline factors:

- 1) Duration of symptoms before trial entry: less than 4 days; more than 4 days; not known
- 2) Clinical diagnosis of pneumonia at trial entry: pneumonia; no pneumonia; not known
- 3) Underlying co-morbid illness at trial entry (defined as any medical illness requiring active regular treatment): underlying co-morbid disease, no underlying co-morbid disease; not known
- Severity of influenza at trial entry (severe influenza defined as the presence of 3 or more community triage criteria [28]): severe influenza; not severe influenza; severity unclear/ not known.

Outcomes will be reported descriptively by sub-group category and treatment arm, and formally estimated by fitting interaction terms in the regression models. It is recognised that power to detect sub-group effects is likely to be low, and these analyses will be regarded as exploratory and interpreted with due caution.

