6.2 Outcome measures

6.2.1 Primary outcome

Admission to intensive care unit or death, within 30 days of admission to hospital.

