6.4.4 Collection of hospital admission data

Once consent has been obtained, routinely available data recorded in hospital notes at the time of hospital admission will be recorded on the Case Report Form (CRF) by site staff. This will include patient contact details, patient demographics, time of onset of symptoms, prior treatment, routinely collected clinical observations and test results.

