9.2 The Number of Participants

The planned sample size of 2200 patients is based on a high severity pandemic along a range of possible scenarios. This flexibility is important as the accuracy of the modelling may only become clear as the pandemic unfolds.

Based on data from the Department of Health, modelling estimates are that, for a high severity pandemic, 35% of those admitted to hospital will die and 25% will be admitted to intensive care. Of those admitted to intensive care, an estimated 50% will die (estimate derived from UK data related to the 2009 pandemic and to community acquired pneumonia). Thus 47.5% will have the composite outcome of death or admission to hospital in the control group. For this scenario, our study would have 90% power to detect a 15% reduction in relative risk of the composite outcome associated with steroids, and a 20% reduction in deaths. Since a high proportion of those admitted to hospital will die and admissions to intensive care will also be high, therefore, an effect size of 15% would be clinically important.

Table 2 presents a range of scenarios centres around a control event rate of 47.5%.

Control event rate	Relative risk reduction with dexamethasone treatment	N* (80% power)	N* (90% power)
35%	20%	1514	2006
	15%	2704	3592
40%	20%	1242	1644
	15%	2210	2932
47.5%	20%	940	1242
	15%	1662	2204
50%	20%	860	1134
	15%	1514	2010

Table 2: Sample size calculations for a high severity pandemic

* Sample size estimates in each cell have been inflated by 5%, to allow for lack of compliance and loss to follow-up (both anticipated to be low)

For low and moderate severity pandemics, a Hazard Ratio of 1.25, indicating an increased risk of discharge at any given time, is considered as the minimum clinically relevant change to detect. The sample size estimation method is the log rank test allowing for competing risks, and assumes that in the control group 5% are censored at 30 days, and in both groups, 6% (low severity pandemic) and 10% (moderate severity pandemic) die during hospitalisation. With 90% power and 1% two-side alpha, and allowing for 5% non-collection of primary outcome data, a total of 912 and 924 participants are required to be randomised for low and moderate severity pandemics respectively.

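### Covariates for the adjusted analyses are chosen by observed imbalance; a short prognostic list fixed in advance would gain precision without new data

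*Protocol*

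**What the plan says.** Section 9.1 of the protocol compares the arms by intention to treat, using regression models that it does not specify further at that point. It then adds: "Secondary analyses will include additional adjustment for variables displaying an important imbalance at baseline". No threshold for an important imbalance is given.

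For a high severity pandemic the composite of section 6.2.1, "Admission to intensive care unit or death, within 30 days of admission to hospital", "will be analysed using generalised linear modelling for binary outcomes, also allowing for stratification by site". For a low or moderate severity pandemic, time to discharge is analysed by "time-to-event regression modelling, also allowing for stratification by site and for the occurrence of death prior to hospital discharge as a competing event". Site is the only baseline factor named in either primary model.

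Prognostic data are nevertheless in hand:
- Section 6.4.4 has sites record "patient demographics, time of onset of symptoms, prior treatment, routinely collected clinical observations and test results".
- Section 12.4 puts date of birth in the database.
- Section 9.1 goes on: "Pre-planned sub-group analyses will be conducted for the primary outcome based on the following baseline factors". It lists symptom duration, pneumonia, co-morbidity and influenza severity, each with a category for unknown values. They are used there only for exploratory interaction tests.

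**The concern.** Observed imbalance is a poor rule for choosing covariates, for three reasons.

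- In a properly randomised trial, imbalance is chance. What adjustment gains depends on how strongly a variable predicts the outcome. A strong predictor that happens to be balanced is left out under this rule, and a weak one that happens to differ is put in.
- With no threshold, two analysts can reach different adjusted models from the same data.
- Between-arm imbalance can be seen only once the data are split by allocation. Section 11 has the Trial Steering Committee approve the SAP before unblinding, so the rule cannot supply a covariate list at that time.

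Two things are at stake: precision in the primary comparison, if site really is the only factor in that model, and the standing of the adjusted analysis as prespecified. Recruitment is meant to finish within one wave of about six weeks (section 9.3), so lost precision may not be recoverable by recruiting for longer.

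**Working it through.** **Inputs from the protocol (section 9.2).** The control event rate is 47.5% (35% deaths + 25% intensive care − half of the 25%). The text reads "Thus 47.5% will have the composite outcome of death or admission to hospital in the control group", but the sum is for intensive care. The relative reduction is 15%, so p0 = 0.475 and p1 = 0.85 × 0.475 = 0.40375, with d = 0.07125. Power is 90% and inflation 5%. Table 2 gives 2204 and the target is 2200.

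**Assumptions.** Alpha is 5% two-sided and allocation 1:1. The protocol states neither for this scenario. With a continuity correction and N/0.95, 5% reproduces all 16 cells of Table 2 within 2 patients. At 1% this cell would be 3095.

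**1. The plan's own figure.** With z = 1.960 and 1.282 and mean rate 0.439375:

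n = [1.960 √(2 × 0.439375 × 0.560625) + 1.282 √(0.249375 + 0.240736)]² / 0.07125² = 1017.6 per arm.

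The continuity correction gives 1045.5, rounded up to 1046. Then 1046/0.95 rounds up to 1102 per arm, or **2204** in total. The stated figure is right for an analysis without covariates.

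**2. Power without adjustment.** 2200 × 0.95 = 2090 analysed, 1045 per arm. Without continuity correction:

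(0.07125 × √1045 − 1.3757) / 0.7001 = (2.3033 − 1.3757) / 0.7001 = 1.325, so power is **90.7%**.

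**3. Gain from adjustment.** Let q0 and q1 be a patient's covariate-specific risks under placebo and dexamethasone. For the marginal risk difference, with N the total and equal arms:

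- unadjusted variance × N = 2 [p0(1 − p0) + p1(1 − p1)]
- adjusted variance × N = 2E[q0(1 − q0)] + 2E[q1(1 − q1)] + Var(q1 − q0)

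Their ratio g is the effective sample size multiplier, close to 1/(1 − R²). Power follows by replacing 1045 with 1045g. The marginal rates are held at 0.475 and 0.40375 throughout.

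Prognostic strength is not in the protocol, so every row below is an assumption. The binary factors are independent, with prevalences of 25% to 50%. The age effect is a log-odds per SD.

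| Assumed covariates | AUC | g | Power |
|---|---|---|---|
| Four factors, OR 1.3; age 0.2 | 0.59 | 1.02–1.03 | 91.4–91.5% |
| Four factors, OR 1.5; age 0.4 | 0.65 | 1.07 | 92.5–92.6% |
| Four factors, OR 2.0; age 0.4 | 0.70 | 1.13–1.14 | 93.7–93.9% |
| Four factors, OR 2.0; age 0.6 | 0.72–0.73 | 1.17–1.18 | 94.4–94.6% |
| One continuous score, log-odds 1.2 per SD | 0.77 | 1.28 | 96.1% |

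Worked row, g = 1.17: 1045 × 1.17 = 1223 per arm; (0.07125 × √1223 − 1.3757) / 0.7001 = 1.594, so power is 94.5%.

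If 20% of values are unknown, the second row falls to about 6% (92.4%) and the third to about 11% (93.5%).

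**4. Cross-checks.** Simulation with a single continuous score gave gains of 1.09, 1.17 and 1.27 at AUC 0.66, 0.72 and 0.77. By the (1 − R²) rule, R² of 5% and 10% gives power of 92.1% and 93.4%.

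**5. Interval width.** 1/√1.02 = 0.990 and 1/√1.17 = 0.925, so the confidence interval is about 1% to 8% narrower. At g = 1.28 it is about 12% narrower (1/√1.28 = 0.884).

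**6. If the event rate is lower.** At a 40% control rate and the same 15% reduction, power without adjustment is 81.1%. With R² = 10% it is 85.0%.

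**The case against.** Section 9 calls itself a summary of a separate SAP. It never says that site is the only term in the primary model, and additional adjustment can mean beyond whatever that model already holds. A SAP naming prognostic covariates there would contradict nothing in the section. This stands: a reader might infer that the protocol rules out covariates in the primary analysis, and it does not. What the protocol does fix is the imbalance rule, and that can be criticised as written.

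The rule governs secondary analyses only, is stated in advance, and looks at baseline data rather than outcomes. This also stands. A reader might call the covariate choice post hoc with respect to results, but the accurate charge is an undefined threshold applied to allocated baseline data.

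A gain of 9% to 27%, as a single continuous score suggests, is the favourable end. Four of the five proposed covariates are two categories plus unknown, and the lower rows of strength are at least as plausible. The comparison also leaves out site, which the primary model already allows for. The range in the verdict reflects the first of these; the second could reduce it further.

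The same gain might be inferred for time to discharge. Nothing supports that. Hazard ratios are non-collapsible, so adjustment changes the target to a conditional hazard ratio and need not narrow its interval. Section 9.2 sizes that scenario on a log-rank test with a hazard ratio of 1.25.

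**Conclusion.** The point holds as one of efficiency and prespecification. The imbalance rule is a poor way to choose covariates, and better candidates are already collected and mostly categorised.

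A reader might infer that the trial is underpowered or its primary analysis invalid. Neither follows: the site-only intention-to-treat comparison is valid, Table 2 reproduces, and the stated 90% power is kept.

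For the binary composite, prespecified adjustment is worth about 2% to 17% more patients (roughly 40 to 355 on 2090 analysed), taking power from about 91% to between 91.5% and 94.5%. About 28% is reached only with strongly predictive covariates. All of this rests on assumed prognostic strength, 5% two-sided alpha, 1:1 allocation, and an unseen SAP that does not already list primary covariates. No magnitude is claimed for time to discharge.

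**What to change.** In section 9.1, delete the sentence on imbalance-driven adjustment and put in its place:

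- **Covariates.** A list fixed in advance: site, age, symptom duration, pneumonia, co-morbidity and influenza severity at entry, with unknown values kept as a category.
- **Symptom duration.** Define it so that exactly 4 days is classified. The present categories are less than and more than 4 days.
- **Binary composite.** Use the list in the primary model, and report the marginal risk ratio and risk difference by standardisation from a logistic model. Give the site-only analysis as a sensitivity analysis.
- **Time to discharge.** The same list can be prespecified, provided the text says that the hazard ratio is then conditional.

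If the SAP already names primary covariates, bring this sentence into line with it.

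The cost is a small edit to section 9.1 and the matching SAP text. No new data are needed, and the at-least-annual review during hibernation (section 6.1) allows the change before any patient is randomised.

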9.2 The Number of Participants

The planned sample size of 2200 patients is based on a high severity pandemic along a range of possible scenarios. This flexibility is important as the accuracy of the modelling may only become clear as the pandemic unfolds.

Based on data from the Department of Health, modelling estimates are that, for a high severity pandemic, 35% of those admitted to hospital will die and 25% will be admitted to intensive care. Of those admitted to intensive care, an estimated 50% will die (estimate derived from UK data related to the 2009 pandemic and to community acquired pneumonia). Thus 47.5% will have the composite outcome of death or admission to hospital in the control group. For this scenario, our study would have 90% power to detect a 15% reduction in relative risk of the composite outcome associated with steroids, and a 20% reduction in deaths. Since a high proportion of those admitted to hospital will die and admissions to intensive care will also be high, therefore, an effect size of 15% would be clinically important.

Table 2 presents a range of scenarios centres around a control event rate of 47.5%.

Control event rate	Relative risk reduction with dexamethasone treatment	N* (80% power)	N* (90% power)
35%	20%	1514	2006
	15%	2704	3592
40%	20%	1242	1644
	15%	2210	2932
47.5%	20%	940	1242
	15%	1662	2204
50%	20%	860	1134
	15%	1514	2010

Table 2: Sample size calculations for a high severity pandemic

* Sample size estimates in each cell have been inflated by 5%, to allow for lack of compliance and loss to follow-up (both anticipated to be low)

For low and moderate severity pandemics, a Hazard Ratio of 1.25, indicating an increased risk of discharge at any given time, is considered as the minimum clinically relevant change to detect. The sample size estimation method is the log rank test allowing for competing risks, and assumes that in the control group 5% are censored at 30 days, and in both groups, 6% (low severity pandemic) and 10% (moderate severity pandemic) die during hospitalisation. With 90% power and 1% two-side alpha, and allowing for 5% non-collection of primary outcome data, a total of 912 and 924 participants are required to be randomised for low and moderate severity pandemics respectively.

The target sample size for the study is 2200. If the pandemic is of low or moderate severity, it is likely that fewer than 2200 participants will be randomised during the first wave of approximately six weeks duration, although this definition will not be available until after the end of the first wave. If more than 924 participants are randomised in a low/moderate severity pandemic then smaller effect sizes may be detectable.

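### The 1% two-sided alpha for time to discharge fits neither the 912/924 participants in its own sentence nor the 95% intervals planned in section 9.1

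*Protocol*

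**What the plan says.** Section 9.2 of the protocol sets the minimum clinically relevant effect for low and moderate severity as "a Hazard Ratio of 1.25, indicating an increased risk of discharge at any given time". The calculation is a log-rank one with competing risks, and it takes 5% of controls as censored at Day 30. For deaths it supposes that "in both groups, 6% (low severity pandemic) and 10% (moderate severity pandemic) die during hospitalisation". The error rates follow: "With 90% power and 1% two-side alpha, and allowing for 5% non-collection of primary outcome data". The result is that "a total of 912 and 924 participants are required to be randomised for low and moderate severity pandemics respectively".

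This 1% is the only significance level stated anywhere in the protocol. For the high-severity composite, section 9.2 says that "our study would have 90% power to detect a 15% reduction in relative risk of the composite outcome associated with steroids" but names no alpha, and neither does Table 2.

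Section 9.1 covers all primary and secondary comparisons together. Results are to be presented as point estimates "with 95% confidence intervals, and exact p-values". It makes no exception for the low/moderate branch.

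**The concern.** A design alpha of 1% and a reported 95% interval point to different thresholds. The protocol does not say which one governs a low/moderate-severity trial, or why 1% was chosen. Section 9.3 plans no efficacy interim that would explain a reduced level.

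The sentence giving the 1% also looks numerically impossible, which raises the question of whether 1% was the level used at all. What is at stake is the interpretation of the primary result and the power claimed for it. Under section 9.1, severity is defined only after the first wave and the analysis follows quickly to inform later waves. A threshold still open at that point would be settled with the data in hand.

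**Working it through.** **Inputs.** From section 9.2: hazard ratio 1.25, 90% power, 1% two-sided alpha, 5% of controls censored at 30 days, 6% or 10% in-hospital deaths, 5% non-collection, N = 912 (low) and 924 (moderate). Assumption: 1:1 allocation, since the ratio is not stated.

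**1. Discharges needed.** E = 4(z_α/2 + z_β)² / (ln HR)², with ln 1.25 = 0.2231, whose square is 0.04979.
- 1% two-sided: 4 × (2.576 + 1.282)² / 0.04979 ≈ 1,195.
- 5% two-sided: 4 × (1.960 + 1.282)² / 0.04979 ≈ 844.

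The 1% requirement exceeds 912 and 924, so no assumption about censoring can rescue it.

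**2. Trying to reproduce 912/924.**
- *5% censoring only.* Probability of discharge is 0.95 in controls and 1 − 0.05^1.25 = 0.976 on treatment, mean 0.963. At 5%: 844/0.963 ≈ 877; 877/0.95 = 923.2, rounded up to 924. This equals the stated moderate figure and is close to the stated low one. At 1% the same steps give about 1,307.
- *Deaths added as competing events, constant cause-specific hazards.* Low: discharge probability 0.890 in controls and 0.925 on treatment, mean 0.908. Moderate: 0.850 and 0.891, mean 0.870. At 5%, N ≈ 980 and 1,020. At 1%, N ≈ 1,390 and 1,450.

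The stated figures are therefore near a 5% calculation and far from a 1% one, but the full stated assumptions do not reproduce them at either level.

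**3. Power at the stated N.** Power = Φ(√E × ln 1.25 / 2 − z_α/2).

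| Case | Discharges | 1% two-sided | 5% two-sided |
|---|---|---|---|
| Low: 912 × 0.95 × 0.908 | 786 | 71% | 88% |
| Moderate: 924 × 0.95 × 0.870 | 764 | 69% | 87% |
| Every analysed patient discharged | 866 / 878 | 76% / 77% | 91% / 91% |

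**4. Results between the two thresholds.** Assume 88% to 92% of those analysed are discharged by Day 30. Discharges then run from 912 × 0.95 × 0.88 = 762 to 924 × 0.95 × 0.92 = 808. The critical hazard ratio is exp(2z/√E): 1.148 to 1.153 at 5% and 1.199 to 1.205 at 1%. Power over this range is 87% to 89% at 5% and 69% to 72% at 1%. The difference, the chance of 0.01 < p < 0.05 at a true hazard ratio of 1.25, is 16% to 18%. With everyone discharged it is 14% to 15%. With 2,200 randomised and 90% of those analysed discharged (2,200 × 0.95 × 0.90 = 1,881 discharges) it is about 1%.

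**5. The alpha behind Table 2.** Use the two-proportion formula with continuity correction, rounded up per arm and divided by 0.95. For 47.5% control rate, 15% relative reduction and 90% power at 5% two-sided, this gives 1,046 per arm; 1,046/0.95 rounds up to 1,102, so the total is 2,204, as printed. All 16 cells come out within 2 participants at 5%. None does at 1%, where this cell would be about 3,094.

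**The case against.** Section 9.1 says that results are presented with 95% intervals and exact p-values. It does not say that success is judged by whether the interval excludes 1, and an exact p-value lets any reader apply a 1% threshold. That is correct. A reader might infer that the protocol makes one result both positive and negative, but this would need a decision rule that section 9.1 does not contain.

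The composite and time to discharge are alternative primaries chosen by pandemic severity, so they may carry different alphas. This also stands. It would be wrong to apply 1% to the composite and conclude that its 90% power fails, because the protocol attaches 1% to the low/moderate calculation only.

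The decision threshold may be set in the statistical analysis plan, which is not at hand. Its absence from the protocol is therefore no finding. But that plan cannot make 1%, 90% power, a hazard ratio of 1.25 and 912/924 consistent with one another.

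The 1% may be a misprint for 5%. If so, the conflict with the 95% interval disappears once it is corrected. That supports correcting the sentence and does not excuse it.

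Finally, section 9.2 keeps the overall target at 2,200 and allows for more than 924 in this branch. The 16% to 18% then shrinks, as step 4 shows.

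**Conclusion.** The point holds in a limited form. The 1% is a stated design figure that is incompatible with the participant numbers in the same sentence and does not match the 95% interval planned for the primary comparison. The first is an arithmetic error under any censoring assumption: about 1,195 discharges are needed from at most 924 people. The second leaves a result between the thresholds open to either reading, without amounting to a formal contradiction.

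In size, power at 912/924 is about 70% at 1%, or about 87% to 89% at 5%, against the stated 90%. The 16% to 18% chance of an ambiguous result depends on 912 to 924 being randomised and on the assumed 88% to 92% discharged.

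A 5% calculation that leaves out deaths fits the printed 924, which makes a misprint plausible. It does not prove one, because 912 is matched only approximately and adding the deaths gives larger numbers. The headline sample size of 2,200 for the composite is not affected.

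**What to change.** Correct the alpha in section 9.2 to the level actually used, and give the primary hazard ratio an interval that matches it.

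- **If 5% is meant:** replace 1% with 5%, keep the 95% interval, and restate power at 912/924 as about 87% to 89% once the stated censoring and deaths are counted. Keeping 90% would need about 980 and 1,020.
- **If 1% is meant:** say that the primary is judged at two-sided p < 0.01, report a 99% interval (a 95% interval may be added as description), and restate power at 912/924 as about 70%. Keeping 90% would need about 1,390 and 1,450.

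In either case, add to Table 2 that it uses 5% two-sided, and bring the later remark in section 9.2 about exceeding 924 into line with any new figure.

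The cost is a few sentences in sections 9.1 and 9.2, made before activation. Choosing 1% also brings a wider primary interval, and either a power about 20 percentage points below the one stated or a larger requirement, which still lies within the 2,200 target.
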